7.3.2 Adverse Events

The applicable definition of an Adverse Event (AE) is in the study protocol section 9.4. A treatment-emergent AE (TEAE) is an event not present prior to exposure to study drug or any pre-existing event that worsens following exposure to study drug. The period for treatment-emergent AE analysis starts from the first exposure to the study drug until the patient exits the study. Adverse events (AEs) will be coded using MedDRA to give a preferred term and a SOC term for each event.

Descriptive summaries (frequencies and percentages) for specific TEAEs will be presented by system organ class and preferred term according to the Medical Dictionary for Regulatory Activities (MedDRA Version 19.1) dictionary. In addition to an overall presentation of all TEAEs, reports will be generated for special classes of TEAEs such as study drug related TEAEs, serious TEAEs, Maximum severity and TEAEs resulting in treatment discontinuation. These reports will be supported by individual patient listings, as necessary.

Adverse events will be counted by the number of events as well as the number of patients. For the summaries which count the number of patients, multiple TEAEs with the same MedDRA preferred term within the same subject will only be counted once.

Document Title:	Statistical Analysis Plan		
Version Number:	1.0	Date:	31 Mar 2020
Protocol Number:	SARO.17.004	Sponsor Name:	Zydus Discovery DMCC

Only patient listings will be provided for AEs that occur after signing informed consent but prior to exposure to investigational product. These listings will comprise all events occurring during this period in any subject who consented to participate in the study.

These listings will at least contain but not limited to information such as onset and resolution times, maximum severity, causal relationship to study treatment and action taken.

7.3.3 Vital Signs

Vital signs parameters include blood pressure, pulse rate, oral temperature and respiratory rates. Vital signs assessments will be performed at screening, baseline, Week 6, Week 12, Week 18, Week 24 and Week 28 visits.

Descriptive summaries (N, mean, median, standard deviation, minimum and maximum values) of absolute (measured) values and change from baseline in each vital sign parameter at each scheduled assessment visit will be presented. A by-patient listing will be provided for all vital sign parameter results (scheduled and unscheduled) for all enrolled patients.

7.3.4 Physical Examination

Physical examination assessments will be performed at screening, baseline, Week 6, Week 12, Week 18, Week 24 and Week 28 visits. A by-patient listing will be provided for all physical examination parameter results (scheduled and unscheduled) for all enrolled patients.

7.3.4 Laboratory Results

Clinical laboratory assessments will be performed at screening, baseline, Week 6, Week 12, Week 18, Week 24 and Week 28 visits. Laboratory values will be presented using the International System of Units (SI units). Clinical laboratory evaluations consist of hematology, clinical biochemistry and urinalysis.

Absolute (measured), absolute (change) and relative (percent change) from baseline values will be summarized descriptively (N, mean, median, standard deviation, minimum, and maximum values) at each assessment for hematology and biochemistry parameters. A summary table of the categorical grade shift changes using the normal ranges from baseline to last study visit will be provided.

Document Title:	Statistical Analysis Plan		
Version Number:	1.0	Date:	31 Mar 2020
Protocol Number:	SARO.17.004	Sponsor Name:	Zydus Discovery DMCC

For summary purposes, each value below/above the limit of quantification (LOQ) will be imputed numerically to the nearest value below/above the limit, respecting the same number of digits than numerical values (e.g. if the number of digit=0, subtract/add 1 to the limit of quantification; if the number of digit =1, subtract/add 0.1 to the LOQ, etc).

A by-patient listing will be provided for all patients with laboratory results (scheduled and unscheduled). In addition, a listing of all clinically significant abnormal values will be provided.

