#### 4.4 SUBJECT WITHDRAWAL

Subjects may withdraw from the study at any time for any reason without prejudice to his or her future medical care. Although a subject is not obliged to give his/her reason for withdrawing prematurely, the PI will make a reasonable effort to obtain the reason while fully respecting the subject's rights. If there is a medical reason for withdrawal, the subject will remain under the supervision of the PI for follow-up of AE(s) as detailed in *Section 9.4.3*. Every effort will be made to continue clinical and/or laboratory follow-up, as appropriate, in subjects who wish to withdraw from the study drug ) and reasonable efforts will be made to contact a subject who fails to attend any follow-up appointments, in order to ensure that he/she is in satisfactory health. A subject's withdrawal of consent and agreement to undergo a final examination will be documented on the case report form (CRF) and on the PI's copy of the ICF, which will be countersigned and dated by the subject.

As far as possible, all assessments scheduled for End-of-treatment must be performed on all subjects who receive the study drug but do not complete the study according to protocol. However, liver biopsy should be performed in those subjects who have completed at least 12 weeks of the study treatment.

	Approved by: [name] [name]	Protocol No.: SARO.17.004.02.PROTOCOL Version No.: 2.0
---	---	---

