- d. Concomitant medication will be assessed.
- e. ECG will be performed.
- f. Safety parameters will be assessed as per Table 1.
- g. Adverse events will be recorded.

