### 8.2.3 Safety Analysis

All safety analysis will be carried out on the safety population. The frequency tabulations of abnormal clinical laboratory values for the parameter will be presented by visit. Summary statistics for clinical laboratory parameters, ECG, physical examination and vital signs will be presented by visit.

All AEs observed during the study period will be listed. Incidence of all AEs reported during the study will be summarized using the Medical Dictionary for Regulatory Activities (MedDRA) (version 19 or higher) by body system, frequency, severity, seriousness and relationship to study drug and expectedness. Frequency and percentage of AEs occur during the course of study will be calculated and presented in the report. All AEs will be assessed for causality, severity and seriousness. The frequency tabulations of abnormal clinical laboratory values for the parameter will be presented by visit. Summary statistics for clinical laboratory findings and vital signs will be presented.

	Approved by: [name] [name]	Protocol No.: SARO.17.004.02.PROTOCOL Version No.: 2.0
---	------------------------------------	---

 Zydus Discovery DMCC	CLINICAL TRIAL PROTOCOL Saroglitazar Magnesium – Phase 2 SARO.17.004	CONFIDENTIAL Page 56 of 76
--	---	---

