1. INTRODUCTION

The purpose of this document is to provide a description of the statistical methods and procedures to be implemented for the analysis of data from SARO.17.004 study. This document is based on protocol version 2.0, dated 02 August 2018. The statistical planning and conduct of analysis of the data from this study will follow the principles defined in relevant International Council for Harmonisation (ICH)-E9 guidelines. This Statistical Analysis Plan (SAP) has been developed prior to database lock or final analysis. Any changes from the planned analysis as described in the protocol are detailed here, and any differences described here supersedes the analysis presented in the protocol. Any deviations from the planned analyses described in this SAP will be documented in the clinical study report, together with the reason for such changes.

Prior to start of any statistical analyses, the database must be authorized and all decisions regarding assignment of patients to study populations must be completed. In addition, protocol deviations must be identified prior to the start of statistical analyses.

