2.2.1 Study design

This is a Phase 2 randomized, multi-center, double-blind, placebo-controlled proof of concept study to evaluate the safety and efficacy of Saroglitazar magnesium 2 mg and 4 mg in patients with NASH meeting pre-specified inclusion/ exclusion criteria. Male and female patients aged 18 to 75 years will be enrolled in this study. Approximately 15 patients who meet the inclusion and exclusion criteria will be enrolled.

Liver biopsy will be performed at the screening visit to confirm the diagnosis of NASH and to record the baseline NAFLD Activity Score. The histological evidence of NASH is defined as $NAS \geq 4$ with a minimum score of 1 for all of its three components [steatosis, hepatocyte ballooning and lobular inflammation].

This study will be conducted over a period of up to 32 weeks and will include a 4-week screening phase, a 24-week treatment phase and a safety follow-up visit, 4 weeks after the last treatment. The study plan is provided below.

Document Title:	Statistical Analysis Plan		
Version Number:	1.0	Date:	31 Mar 2020
Protocol Number:	SARO.17.004	Sponsor Name:	Zydus Discovery DMCC

[figure not shown]
NOTE: Liver biopsy showing NASH within 6 months preceding Visit 1 can be used.

The study visits are planned at screening [-4 Week (-28 days)], Baseline/Enrollment Visit (Day 1 ± 7 days), Week 6 (Day 43 ± 7 days), Week 12 (Day 85 ± 7 days), Week 18 (Day 127 ± 7 days), Week 24 (Day 169/ ± 7 days) and a safety follow-up visit at Week 28 (Day 197 ± 7 days). All patients will be advised to follow a stable lifestyle. No change in the intensity of lifestyle (Diet/Exercise) will be allowed during the study period.

Document Title:	Statistical Analysis Plan		
Version Number:	1.0	Date:	31 Mar 2020
Protocol Number:	SARO.17.004	Sponsor Name:	Zydus Discovery DMCC

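### The SAP's only laboratory shift table ends at the last study visit, which is off drug for patients who attend Week 28, so on-drug category changes that have reverted by then show as no shift

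*SAP*

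**What the plan says.** SAP 7.3.4 (Laboratory Results) specifies a single categorical shift table: "A summary table of the categorical grade shift changes using the normal ranges from baseline to last study visit will be provided". It gives no second version ending at Week 24, at the last on-treatment value or at the worst on-treatment value. The same section sets the schedule: "Clinical laboratory assessments will be performed at screening, baseline, Week 6, Week 12, Week 18, Week 24 and Week 28 visits".

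SAP 2.2.1 describes the final visit as "a safety follow-up visit, 4 weeks after the last treatment" and counts it within a study of up to 32 weeks. Protocol 7.2 says of Visit 7: "Safety parameters will be assessed as per Table 1". Table 1 is not in the text available for review, so the Week 28 laboratory tests rest on the SAP schedule, and the point is not tied to any one analyte.

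For patients who do not complete, Protocol 4.4 asks, as far as possible, that "all assessments scheduled for End-of-treatment must be performed on all subjects who receive the study drug but do not complete the study". Protocol 4.4 and 4.5 also ask for continued clinical and laboratory follow-up after study drug stops. Protocol 4.6 has patients stopped for safety followed until the event resolves.

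Other laboratory output in SAP 7.3.4 comprises descriptive summaries at each assessment for hematology and biochemistry, a listing of all results including unscheduled ones, and a listing of clinically significant abnormal values. Protocol 8.2.3 adds: "The frequency tabulations of abnormal clinical laboratory values for the parameter will be presented by visit".

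**The concern.** A shift table is usually read as an account of how many patients changed laboratory category while on treatment. This one, as worded, reports status at the end of follow-up. In a 24-week placebo-controlled study, a change that appears on drug and resolves after stopping is of direct interest for safety, and this end point removes it from the table. A change that appears only after stopping enters the table on the same footing as one that arose on drug.

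The end point may also fall at different times from last dose in different patients, depending on whether a patient completes, leaves early, or is followed after stopping. With planned arms of 6, 6 and 3, a single patient shown as unshifted is one of 6 or one of 3, so the table's end point matters to how it reads.

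**Working it through.** **Inputs.** Visit 6 is Day 169 ± 7 days and Visit 7 is Day 197 ± 7 days (Protocol 7.1). Screening lasts 4 weeks, treatment 24 weeks, and follow-up comes 4 weeks after the last treatment (SAP 2.2.1).

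**The plan's own timeline reproduces.** 4 + 24 + 4 = 32 weeks, and 197 − 169 = 28 days = 4 weeks.

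**Range across the windows.** Visit 6 can fall on Days 162 to 176 and Visit 7 on Days 190 to 204. The shortest interval is 190 − 176 = 14 days and the longest is 204 − 162 = 42 days. If dosing ends at Visit 6, every permitted Week 28 sample is at least 14 days off drug.

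**Whether the last study visit could mean the last on-treatment visit.** Nothing in SAP 7.3.4 restricts it so. Protocol 5.8.1 treats the safety follow-up as the end of the study. SAP 7.3.1 defines study duration by the last visit and treatment duration by the last dose, so the SAP separates the two ideas elsewhere. For a patient who attends Week 28, the last study visit is Week 28.

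**What the table shows for a patient in range at baseline who attends Week 28:**

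| On drug (Weeks 6 to 24) | Week 28 | Planned table | On-treatment shift |
|---|---|---|---|
| Out of range at some visit | In range | No shift | Shift |
| In range throughout | Out of range | Shift, not marked as off drug | No shift |
| Out of range at some visit | Out of range | Shift | Shift |
| In range throughout | In range | No shift | No shift |

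The first two rows are the ones that mislead.

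**What the other outputs recover.**
- Clinically significant laboratory changes are to be reported as adverse events (Protocol 9.4.1; see also 6.4). SAP 7.3.2 counts treatment-emergent events by patient, with repeats of a preferred term counted once, from first exposure to study exit. A change of this kind stays counted even if it resolves.
- Summaries at each visit show minimum and maximum for hematology and biochemistry, but not how many patients changed category.
- By-visit abnormal frequencies count patients at each visit. They do not say who was already abnormal at baseline. The number of distinct patients across visits is known only to lie between the largest single-visit count and the smaller of the arm size and the sum of the counts.
- Urinalysis has no by-visit summary in the SAP. If the shift table covers urinalysis, it is the SAP's only summary table for it.

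**What remains missing** is the count, per arm, of patients with an on-drug category change that was not reported as an adverse event and had reverted by the last visit.

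**A point for the remedy.** Twenty-four weeks is 24 × 7 = 168 days, so a course starting on Day 1 nominally ends on Day 168, one day before Visit 6. No drug is dispensed at Visit 6, although Protocol 5.2 provides for on-site dosing on visit days. An on-treatment window cut at the last dose date could therefore drop the Week 24 sample.

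**The case against.** The strongest case is that this is a matter of preference. The table is openly labelled with its end point, and the protocol promises no shift table, so the SAP contradicts nothing. SAP 7 analyses safety on a treatment-emergent basis and SAP 7.3.2 runs the adverse-event period to study exit, so including follow-up fits the SAP's general approach. With 15 patients and full listings, any count can be rebuilt by hand.

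Much of this stands, and it limits the weight of the point. It does not remove it. The treatment-emergent rule keeps an event that later resolves, whereas a last-visit end point drops it. Running the period to study exit also does not make a Week 28 value an on-drug one.

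Three stronger readings are tempting, and the documents do not support them:
- A reader might infer that on-drug laboratory abnormalities would go unreported. They would not: adverse-event tables, visit summaries and listings still carry them. The protocol's by-visit abnormal frequencies also remain. The SAP says "any differences described here supersedes the analysis presented in the protocol", and not repeating a tabulation is not describing a difference.
- A reader might infer a systematic split, with early leavers contributing on-drug values and completers off-drug ones. End-of-treatment assessments for early leavers make different timings possible. But the follow-up asked for in Protocol 4.4, 4.5 and 4.6 means an early leaver's last value may be off drug too.
- A reader might want a proportion of patients affected. Any such figure would rest on assumed shift and reversion rates that the documents do not give.

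**Conclusion.** The point holds as a minor one. For patients who attend Week 28, the only laboratory shift table ends on a value taken nominally 28 days (14 to 42) after the Week 24 visit and about 4 weeks after last treatment. It can show a reverted on-drug change as no shift and an off-drug change as an unmarked shift. Early leavers may contribute an end point at a different time from last dose, though not necessarily on drug.

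The damage is confined to this table. No data are lost, and changes judged clinically significant are still counted per patient as adverse events. The conclusion rests on the ordinary meaning of the last study visit and on laboratory tests being done at Week 28 as SAP 7.3.4 states. The number of patients affected cannot be derived from the documents.

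**What to change.** In SAP 7.3.4 (Laboratory Results), replace the last-study-visit end point with two stated ones:

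- (a) Baseline to worst on-treatment value, with worst low and worst high shown separately and unscheduled tests included. Define the on-treatment window to include the Week 24 or end-of-treatment sample (Visit 6 or the early-termination visit), and do not cut it at the last dose date.
- (b) Baseline to Week 24 or end of treatment.

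Show Week 28 separately, labelled as off-drug follow-up, with its own N.

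The cost is a short change of SAP wording and a few more table columns, all from data already planned for collection. The downside is that (a) also counts single transient excursions, which is why (b) should stand beside it.

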2. STUDY OBJECTIVES AND DESIGN

2.1 Study Objectives

Primary Objective

The primary objective of this study is to evaluate the changes in Non-alcoholic Fatty Liver Disease (NAFLD) Activity Score (NAS) at week 24 from baseline and with no worsening of fibrosis in Non-alcoholic Steatohepatitis (NASH) patients.

Secondary Objectives

The secondary efficacy objectives of this study are:

- To evaluate the percentage of responders in the treatment groups.
- To evaluate the percentage of responders, defined as the disappearance of steatohepatitis over the time period up to Week 24 in patients treated with Saroglitazar Magnesium 2 mg and 4 mg.

Document Title:	Statistical Analysis Plan		
Version Number:	1.0	Date:	31 Mar 2020
Protocol Number:	SARO.17.004	Sponsor Name:	Zydus Discovery DMCC

- Changes from baseline to Week 24 in Saroglitazar Magnesium 2 mg and 4 mg for the following parameters:
 - Stage of steatosis, lobular inflammation and ballooning
 - Stage of fibrosis
 - Liver function tests (ALT, AST, ALP, GGT, Direct bilirubin, Total proteins and Albumin).
 - Lipids profile parameters (TG, TC, sdLDL, HDL, LDL, VLDL, non-HDL, ApoA1 and ApoB)
 - Insulin resistance and glycemic control parameters (FPG, HbA1c, Fasting insulin, C-peptide, Adiponectin, HOMA-B and HOMA-IR).
- To assess the safety of Saroglitazar Magnesium 2 mg and 4 mg in patients with non-alcoholic steatohepatitis over 24 weeks of treatment.

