7. SAFETY ANALYSIS STRATEGY

Safety analyses will be conducted using the safety population on a treatment-emergent basis.

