7.2 Safety Hypothesis

There are no formal safety hypotheses in this study. The focus of the safety analysis will be a comprehensive descriptive assessment of the safety endpoints listed in Section 7.1.

Document Title:	Statistical Analysis Plan		
Version Number:	1.0	Date:	31 Mar 2020
Protocol Number:	SARO.17.004	Sponsor Name:	Zydus Discovery DMCC

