7.3.1 Extent of Exposure

Study duration is defined as the date of last visit minus date of informed consent date plus one. Treatment duration is defined as the date of last dose minus the date of the first dose plus one. If the date of last dose is not available, the date of the last visit will be used in the calculation. If the date of first dose is not available, the date of baseline visit will be used in the calculation. Study duration and the treatment duration will be summarized descriptively.

Treatment compliance is calculated as the total number of tablets taken divided by the expected number of tablets to be taken during the study period multiplied by 100. Treatment compliance will be summarized descriptively. In addition, a categorical summary of compliance will also be presented using the following categories: < 80% 80% to 120% and >120%. A subject's is considered to be compliant, if he/she takes 80% to 120% of the study drug during the study period.

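### The only laboratory shift table ends at the last study visit, off drug for completers, and no planned summary gives the worst post-baseline shift or a per-arm count by Protocol 4.6 liver criterion

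*SAP*

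**What the plan says.** SAP 7.3.4 (Laboratory Results) schedules laboratory tests at screening, baseline and Weeks 6, 12, 18, 24 and 28. It plans descriptive statistics at each assessment and one shift table: "A summary table of the categorical grade shift changes using the normal ranges from baseline to last study visit will be provided". It does not say what a grade is. It also plans a by-patient listing of scheduled and unscheduled results and a listing of clinically significant abnormal values.

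The last visit is off drug. SAP 2.2.1 describes it as "a safety follow-up visit, 4 weeks after the last treatment". SAP 7.3.1 keeps visits apart from doses: "Study duration is defined as the date of last visit minus date of informed consent date plus one", while treatment duration runs to the last dose. Last study visit therefore reads as a visit, not as the end of dosing.

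Three statements set the aim. The safety objective (SAP 2.1) is to assess the drug "in patients with non-alcoholic steatohepatitis over 24 weeks of treatment". SAP 7 states: "Safety analyses will be conducted using the safety population on a treatment-emergent basis". SAP 7.2 promises a "comprehensive descriptive assessment of the safety endpoints listed in Section 7.1".

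Protocol 4.6 sets liver rules for stopping or interrupting study drug, mostly as multiples of baseline:
- ALT or AST above 3x baseline, when baseline is at least 1.5x but below 5x ULN.
- ALT or AST above 2x baseline, with total bilirubin above 2x baseline or an INR increase above 0.2.
- ALT/AST elevation with listed symptoms.

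Protocol 8.2.3 adds one further laboratory output: "The frequency tabulations of abnormal clinical laboratory values for the parameter will be presented by visit".

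**The concern.** The shift table is the only categorical laboratory summary that the SAP itself plans. For completers its endpoint is the one scheduled visit at which the drug is no longer taken, so a liver enzyme rise that appears on drug and settles after dosing stops is not visible in it.

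The normal-range scale adds a second limit. Protocol 4 describes recruits as having raised liver tests, although the inclusion criteria in Protocol 4.2 do not require this. Exclusion criterion 8d in Protocol 4.3 admits ALT and AST up to 200 IU/L. A patient who enters above ULN starts in the top category and cannot move higher, whatever the drug does. Protocol 4.6 avoids this by measuring against baseline; the shift table does not.

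At stake is whether someone reading only the summary tables can see how many patients in each arm met the protocol's own liver criteria. In the worst case the shift table suggests improvement in a patient who met one.

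**Working it through.** The documents give no figure to reproduce on this point. The check compares the table's time point with the visit schedule, runs constructed cases through it, and then asks what the other planned outputs add.

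**Visits used.** Post-baseline laboratory visits (SAP 7.3.4) are Weeks 6, 12, 18 and 24 on treatment and Week 28 off treatment. A completer's shift uses 1 of 5, and 0 of the 4 on treatment. Visit days (Protocol 7.1) are 169 and 197, each with a window of 7 days either way:
- Nominal gap: 197 − 169 = 28 days.
- Shortest: (197 − 7) − (169 + 7) = 14 days.
- Longest: (197 + 7) − (169 − 7) = 42 days.

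**Three constructed ALT cases.** ULN is taken as 40 IU/L. This is an assumption, because the range in Protocol Appendix 3 is not readable.

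| Case | Baseline | Peak on drug | Last visit | Peak/baseline | Peak/ULN | Last-visit shift | Worst-value shift |
|---|---|---|---|---|---|---|---|
| A | 80 | 241 | 38 | 241/80 = 3.01 | 241/40 = 6.03 | high to normal | high to high |
| B | 80 | 241 | 70 | 3.01 | 6.03 | high to high | high to high |
| C | 35 | 130 | 36 | 130/35 = 3.71 | 130/40 = 3.25 | normal to normal | normal to high |

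The last-visit table shows improvement for A and no change for B and C. A worst-value shift corrects C but not A or B, which need a count against baseline. A and B start at 80/40 = 2.0x ULN, so the >3x rule applies to them. C starts at 35/40 = 0.875x ULN, so it does not.

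The tabulated categories are the same for any ULN from 38 to just below 70. The >3x rule applies to A and B while ULN is at most 80/1.5 = 53.3.

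**What the other planned outputs add.**
- *By-visit maximum percent change (SAP 7.3.4).* Case A at a scheduled visit gives (241 − 80)/80 = +201%, so the arm's maximum exceeds +200%. It does not say how many patients exceeded it, or whether the baseline condition held: C gives (130 − 35)/35 = +271% without falling under the rule.
- *By-visit abnormal frequencies (Protocol 8.2.3).* Take an arm of 6 with baseline ALT 80, 60, 55, 50, 30, 28. Four of 6 exceed 40. If the first value becomes 241 and the others stay the same, the count is still 4/6. C would be caught, since its on-treatment value is newly abnormal.
- *One analyte at a time.* In an arm of 6, let one patient's ALT rise 150% and one patient's bilirubin rise 120%, with all other changes zero. ALT: mean 150/6 = 25.0, SD √[(125² + 5×25²)/5] = 61.24, maximum 150. Bilirubin: mean 120/6 = 20.0, SD √[(100² + 5×20²)/5] = 48.99, maximum 120. These figures are identical whether the two rises are in the same patient or in different patients, yet the number with both above 2x baseline is 1 or 0.
- *TEAE tables (SAP 7.3.2) and discontinuation reasons (SAP 5).* These count patients by term or reason, not by liver criterion.
- *By-patient listing (SAP 7.3.4).* ALT, AST, total bilirubin and INR are all in the safety panel (Protocol Table 4), so a joint rise can be read here, including one seen only at an unscheduled draw.

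**The case against.** The case for leaving the plan alone is substantial, and most of it stands as a limit on the point.

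- **The data are reported.** With about 15 patients, a hand count from the by-patient listing is feasible. A reader might infer that no planned output shows ALT/AST rising with bilirubin or INR in one patient. That is not so: the listing does. What is missing is a summary.
- **On-treatment peaks are not lost.** By-visit maxima and abnormal frequencies would reveal most of them. The SAP says that "any differences described here supersedes the analysis presented in the protocol", but it describes no difference from Protocol 8.2.3 on abnormal frequencies. Silence is not a change, so I take that tabulation as kept.
- **Stopping-rule cases should reach the TEAE tables.** Protocol 6.4 makes an abnormal result reportable if it needs further diagnostic testing or leads to a dosing change or discontinuation, and non-reporting must be justified. Protocol 9.4.1 adds clinically significant laboratory findings.
- **Week 28 is within the treatment-emergent period.** SAP 7.3.2 runs that period for AEs from first exposure until the patient exits the study. A reader might infer that a Week 28 endpoint contradicts the treatment-emergent basis, or that a short on-treatment window should replace the last visit. The documents support neither. Replacement would also drop late or persistent rises. The argument supports including Week 28, not using it alone.
- **Early stoppers are uncertain.** Protocol 4.6 follows them until values resolve or lose clinical significance, while Protocol 4.4 asks for end-of-treatment assessments. Whether their last visit would show a resolved value cannot be known from the documents.
- **Scale of the study.** There are no safety hypotheses, a data monitoring committee reviews safety during the trial (Protocol 7.4), and Protocol 4.6 is a patient-management rule, not an endpoint. This lowers the priority. It does not make the last visit alone a good endpoint for the shift table.

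**Conclusion.** The point holds as a cheap improvement of modest priority. For completers, the only planned laboratory shift table rests on a single off-drug value, nominally 28 days after the Week 24 visit. It can show no change or improvement for a patient whose ALT more than tripled on drug. No planned summary table gives the worst post-baseline shift, a per-arm count by Protocol 4.6 liver criterion, or concurrent ALT/AST with total bilirubin or INR elevation.

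It does not follow that a liver signal would go unreported, since the listing and the AE route carry it. Nor does the point touch efficacy, sample size or any error rate.

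The time-point limit follows from the text of the SAP for anyone who completes follow-up. The scale limit assumes that *grade* means low, normal or high. If it means bands of ULN, the scale limit weakens and the time-point limit stays. The ALT values, the ULN of 40 IU/L and the joint-rise example are illustrations. How many patients enter above ULN is not known from the documents.

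**What to change.** In SAP 7.3.4 (Laboratory Results):

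1. Keep the last-visit shift table. Beside it, add a shift from baseline to the worst post-baseline value, using scheduled and unscheduled results over the treatment-emergent period of SAP 7.3.2. Make values through Week 24 or last dose identifiable as on treatment. Define *grade*.
2. Add one table by arm, with denominators and a supporting listing that flags the patients, counting those with:
   - ALT or AST above 3x baseline, among patients whose baseline for that enzyme was 1.5x to below 5x ULN;
   - ALT or AST above 2x baseline with, on the same sampling date, total bilirubin above 2x baseline or an INR rise above 0.2.

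   Add a footnote that the symptom-based rule in Protocol 4.6 is not covered by this table.

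The cost is SAP wording and a little programming on data already collected. No visit, sample or efficacy analysis changes.

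The drawback is very small denominators, at most 6, 6 and 3, so counts of 0 or 1 need cautious reading. A count of zero has a one-sided 95% upper limit of 1 − 0.05^(1/6) = 39% in an arm of 6 and 1 − 0.05^(1/3) = 63% in the arm of 3. The table should therefore be presented as a description of cases, not as evidence that liver risk is absent.
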